serve as the control site in which training will be provided via the virtual/remote training lead by a trained OT; 5 PACE organizations will serve as the comparison and be trained through the online training site. Prior to randomization, we will carefully examine PACE organizations on important variables such as size, location (urban; rural) percent of persons with dementia, and staff: participant ratio. In each site, one occupational therapist (OT) and one nurse (RN) will be trained (e.g., 5 OTs and 5 RNs in virtual/remote training sites; 5 OTs and 5 RNs in online training sites for a total of 10 OTs and 10 RNs or 20 health providers) Re-randomization procedures. Because COPE will be delivered by PACE staff to multiple participants with dementia within each organization, randomization at the individual participant level could lead to significant contamination between treatment and control conditions within an organization. Prior to randomization, we will collect organization-level data and have measures of organization size (or capacity), location (urban, suburban, rural), and summary characteristics of the participant population at each organization (e.g., percentage with dementia diagnosis, percentage minority). Because we will randomize ten organizations to five virtual/remote and five online training organizations, notable and problematic imbalances on at least a few organization-level characteristics could easily occur by chance in a single randomization. Methodological innovations are needed to achieve balance on these multiple organization-level characteristics while still maintaining the experimental rigor and inferential value of true random assignment. [name] will implement a re-randomization approach to achieve these important methodological goals. The balance match weighted (BMW) design is an innovative re-randomization procedure that is particularly well suited to our goals (54). Using the BMW approach, we will: 1) finalize the list of important covariates for which we desire matching or balancing across intervention and control organizations, 2) generate 20 lists of random assignments for these 10 organizations into intervention and control conditions, 3) calculate propensity scores of intervention assignment as a function of the covariates, and 4) select the random assignment list that minimizes the propensity score differences between intervention and control organizations. The BMW approach provides a random assignment distribution that has an optimal balance on multiple organization-level characteristics. This will result in even greater control over potential covariate influences and provide somewhat greater power to detect a COPE program effect. Treatment Conditions: COPE Online Training: Trinity PACE Organizations assigned to the COPE Online Training will receive the 10- Module training program described above. Designated OT/ RNs at the assigned PACE Organization will be emailed unique log-in details and instructions for completing the online training within the 3-day training window (to align with control group training) but at their own pace. Log-in details including date, time and duration in training sessions will be tracked. COPE Virtual/Remote Training: We will train one OT and one RN at each of the five PACE organizations randomly assigned to the virtual/remote training. [name] will conduct trainings. Our training program will involve up to 3 days which include about 4 hours of initial readings, PowerPoint presentations, and case presentations. Training will take place via web conference (via GoToMeeting.com or other platform) sessions. We will offer three of these training sessions to accommodate COPE staff members' schedules and assure an interactive process. Further, interventionists will participate initially in monthly tele-conference or web conference sessions and then 6 times a year over the duration of intervention delivery. Sessions will involve case presentations, troubleshooting, and adherence monitoring. We have used this approach in multi-organization endeavors with up to 15 interventionists actively participating by telephone. Using a structured agenda and assigning case presentations a priori facilitates productive discussions. We have allocated funds for COPE staff members time to participate in training and follow-up bimonthly calls to troubleshoot cases. Both groups will participate in monthly debriefing sessions which will be recorded and used to understand type of questions asked, problems encountered etc., to compare the two training groups. We have a specific agenda and methodology for interventionists to provide case reports (55). We will also establish a password secure and encrypted email list serve for interventionists to post challenges and receive feedback from PIs and other interventionists.

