
**PHASE 3 (Aim 3): Efficacy of COPE on PACE participant outcomes by type of COPE training.**  
This aim will be accomplished by evaluating dyad outcomes of the COPE program under the two different training approaches. Following training, each of the PACE organizations will enroll 5 persons with dementia and their caregivers in the study. This will yield 50 family dyads (25 dyads in traditional training sites and 25 dyads in online training sites). At 4 months, all dyad study outcomes will be assessed

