### **Analysis Plan**

Analysis of Aim 1: To compare the training programs on Interventionist uptake. We will conduct pre and

post surveys to assess changes in knowledge and assess satisfaction with the training. COPE interventionists will need to demonstrate Knowledge and Competency in treatment delivery to be certified by Pis and [name] in COPE delivery, a measurement approach we use effectively in our trials (56). We will conduct a noninferiority analysis to determine if online training compared to virtual/remote training results in same or better in Knowledge and Competency scores. Independent-samples t-test, 2 test, and Fishers exact test will be used to compare the groups.

**Analysis of Aim 2:** The fidelity model will be used to compare sessions delivered by interventionists under the two different conditions (online versus virtual/remote training conditions). The accuracy of the computationally derived best model automatic summarization fidelity ratings (excellent, acceptable, problematic) will be evaluated against human ratings for all recorded session (N=600). The comparison of the automated fidelity relative to human fidelity rating will be evaluated through a comparison of agreement (Kappa coefficient). Human ratings will be conducted by Drs [name] and [name] using the COPE Adherence Scale (1= excellent, .5 = acceptable, 0=problematic).

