**Analysis of Aim 3:** To compare the efficacy of COPE on participant outcomes. One-sided to-sample t-tests will be used to examine non-inferiority at 4-months. Upper and lower 95% confidence intervals will be presented for means and medians. Assumptions of normality and equality of variance between groups will be evaluated using Shapiro-Wilk and modified Levene's tests, respectively. Should the variances be unequal, the Aspin-Welch unequal variance t-test will be used to examine non-inferiority; should the normality assumption be violated, the non-parametric Mann-Whitney U test will be used to examine non-inferiority. Descriptive statistics including measures of central tendency (mean, median, mode) and variation (standard deviation, interquartile range, range) for continuous measures as well as frequencies and percentages for dichotomous and categorical variables will be run for all measures at each timepoint. Outliers will be assessed by visual inspection of distributions and checked for accuracy. Histograms and Q-Q plots will be used to evaluate assumptions visually. Two-sample t-tests (or non-parametric Wilcoxon tests, as necessary) and Fisher's exact tests will be used to examine differences in demographic and treatment variables between intervention groups at each timepoint. To demonstrate that the online COPE training intervention is the same or better than the virtual/remote training intervention with regards to participant outcomes, one-sided two-sample t-tests will be used to examine non-inferiority at 4 months. Upper and lower 95% confidence intervals will be presented for means and medians. Assumptions of normality and equality of variance between groups will be evaluated using Shapiro-Wilk and modified Levene's tests, respectively. Should the variances be unequal, the Aspin-Welch unequal variance t-test will be used to examine non-inferiority; should the normality assumption be violated, the non-parametric Mann-Whitney U test will be used to examine non-inferiority.

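### Ten PACE organizations are randomized, but the Aim 3 non-inferiority tests and confidence intervals treat 50 dyads as independent

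*Combined protocol and SAP*

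**What the plan says.** The unit of allocation is the organization. Under Study Procedures, Phase 2, the re-randomization paragraph reads "Because we will randomize ten organizations to five virtual/remote and five online training organizations". The stated reason is contamination: "Because COPE will be delivered by PACE staff to multiple participants with dementia within each organization", patients at one site could not safely be split between conditions. The staffing is one pair per site: "In each site, one occupational therapist (OT) and one nurse (RN) will be trained". The allocation is restricted. Twenty lists are generated, and the last step is to "select the random assignment list that minimizes the propensity score differences between intervention and control organizations".

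Under Phase 3 (Aim 3), "each of the PACE organizations will enroll 5 persons with dementia and their caregivers in the study", which gives 25 dyads per arm.

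The Analysis Plan for Aim 3 then says that "one-sided two-sample t-tests will be used to examine non-inferiority at 4 months". If variances differ, the Aspin-Welch test replaces the t-test; if normality fails, Mann-Whitney does. On intervals it says: "Upper and lower 95% confidence intervals will be presented for means and medians". There is no site term, mixed model, cluster-robust variance, site-level summary, randomization test or ICC in the text available.

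For Aim 1 the plan says: "Independent-samples t-test, 2 test, and Fishers exact test will be used to compare the groups". For Aim 2 it names only a kappa for automated against human ratings, and no test for the comparison between training conditions.

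**The concern.** All five dyads at a site share the same trained OT and RN and the same organization, so their outcomes are likely to be positively correlated. The contrast between training methods varies between sites: with ten sites in two arms it has 10 - 2 = 8 degrees of freedom, whereas the planned t-test claims 50 - 2 = 48. The two fallbacks assume independence just as the t-test does, and the planned Shapiro-Wilk and Levene checks cannot detect the problem.

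The direction matters in a non-inferiority trial. Too small a standard error favors the conclusion the investigators hope for, that online training is as good. The Interim Analyses text under Data and Safety Monitoring calls dyad outcomes secondary, but gives them the role of confirming, or not, the comparison of training methods.

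**Working it through.** **Inputs from the document.** Sites per arm k = 5; dyads per site m = 5; one-sided test; 95% intervals. The plan's own sample size reproduces: 10 x 5 = 50 dyads and 5 x 5 = 25 per arm.

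**Assumptions.** The ICC is not given; 0.01 to 0.20 is shown. The one-sided level is not given; 2.5% and 5% are shown. No Aim 3 margin is stated, but the error at the margin does not depend on its value. Outcomes are normal with total SD 1.

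**Dyad-level t-test.** The design effect is DE = 1 + (m - 1) x ICC = 1 + 4 x ICC. The arm difference has true variance 2 x DE/25. The pooled variance used by the test is distributed as V = [DE x chi2(8) + (1 - ICC) x chi2(40)]/48. The true one-sided error is the average, over V, of 1 - Phi(t48 x sqrt(V/DE)), where t48 is the nominal critical value. Coverage of the two-sided 95% interval for the arm difference is 100% minus twice the error at nominal 2.5%. In this table the balanced covariates are taken to explain none of the site variance.

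| ICC | DE | Error, nominal 2.5% | Error, nominal 5% | 95% CI coverage |
|---|---|---|---|---|
| 0.01 | 1.04 | 2.7% | 5.3% | 94.5% |
| 0.05 | 1.20 | 3.7% | 6.7% | 92.6% |
| 0.10 | 1.40 | 4.9% | 8.3% | 90.1% |
| 0.20 | 1.80 | 7.4% | 11.3% | 85.2% |

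Simulation of 200,000 trials per setting agrees (for example 8.3% at ICC 0.10, nominal 5%). The Mann-Whitney fallback gives 3.4%, 4.4% and 6.7% at nominal 2.5% for ICC 0.05, 0.10 and 0.20.

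**Effect of the best-of-20 allocation.** This was simulated with four normal site covariates. Mahalanobis distance stood in for the propensity-score criterion, so the decimals are approximate. Entries are one-sided error at nominal 2.5% for ICC 0.05 / 0.10 / 0.20.

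| Site variance explained by balanced covariates | Planned dyad-level test | t-test on ten site means |
|---|---|---|
| None | 3.7 / 4.9 / 7.4% | about 2.5% |
| Half | about 3.1 / 3.8 / 5.1% | about 2.1 / 1.9 / 1.5% |
| All | about 2.6-2.7% | about 1.7 / 1.2 / 0.7% |

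**Precision of the site-mean analysis.** The planned half-width is 2.011 x sqrt(2/25) = 0.57 SD. With 8 degrees of freedom it is 2.306 x sqrt(2 x DE/25) = 0.71, 0.77 and 0.88 SD at ICC 0.05, 0.10 and 0.20. From the noncentral t, with no true difference, the margin that can be ruled out with 80% power moves as follows:

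- One-sided 5%: from 0.71 SD to 0.84, 0.91 and 1.03 SD.
- One-sided 2.5%: from 0.81 SD to 0.99, 1.07 and 1.21 SD.

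**Aim 1.** With two staff per site and nominal 2.5%, the independent-samples test has error 3.0% (ICC 0.10) and 3.7% (ICC 0.20) if OTs and RNs do not differ on average. With an assumed OT-RN gap of 0.8 SD it has 2.2% and 2.7%. The error can go either way.

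**The case against.** The size of the problem rests on an ICC that the document does not give. At 0.01 the error is 2.7% against 2.5%, which nobody would notice; it becomes material from about 0.05. That stands. The direction of the error is certain for any positive ICC, but its importance is not.

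The main figures take the balancing covariates to be worthless, although they are to be chosen as important. That stands in part. If they explain half of the site variance, error at ICC 0.10 is about 3.8%, not 4.9%. It is close to nominal only if they explain all of it. Balancing on size, location and case mix cannot balance how well a particular OT-RN pair delivers COPE.

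The unadjusted site-mean test is conservative under this allocation, clearly so (down to about 0.7%) when the covariates explain everything. That stands as a cost of the remedy.

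The dyad outcomes are secondary in an early-stage study, and without a margin no non-inferiority decision can be made anyway. The missing margin is a separate gap that also needs filling. It does not excuse an interval that is too narrow. The plan attaches its intervals to means and medians, not expressly to the arm difference, but coverage for an arm mean is about the same (about 90.2% at ICC 0.10).

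Two parts of the document (directly before the account of the earlier COPE trial) were not available, so the absence of a site adjustment is established only for the text supplied.

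**Conclusion.** The concern holds for Aim 3. The analysis as written does not match the unit of randomization, and this is an error in what is specified, not merely a missing detail. At ICC 0.05 to 0.20 the true one-sided error is 3.7% to 7.4% at nominal 2.5% (6.7% to 11.3% at nominal 5%), and coverage falls to between 92.6% and 85.2%. If the balanced covariates explain half of the site variance, the range at nominal 2.5% is about 3.1% to 5.1%. These sizes rest on the assumed ICC and level; the direction does not. It must be fixed before the Aim 3 analysis. For Aim 1 the same oversight is minor. For Aim 2 no between-arm test is stated, so no error rate can be attached to it.

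**What to change.** In the Analysis Plan for Aim 3, replace the dyad-level tests with the following.

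- **Primary analysis:** for each dyad outcome, a two-sample t-test on the ten site means (8 degrees of freedom). The non-inferiority bound and the 95% interval for the arm difference come from it. State the margin and the one-sided level.
- **If normality is doubtful:** a permutation test of the ten site means, after shifting one arm by the margin, in place of Mann-Whitney on dyads.
- **Mixed model:** acceptable only if the site effect stays in the model, with between-site degrees of freedom, when its variance is estimated as zero. The estimate is non-positive with probability P(F(8,40) <= (1 - ICC)/(1 + 4 x ICC)) = 39%, 26% and 11% at ICC 0.05, 0.10 and 0.20. Dropping site in those trials would bring back the planned test.
- **Sensitivity analysis:** a randomization test that repeats the best-of-20 selection, because the site-mean test can be conservative. It has a limit that the SAP should state. Ten sites split 5 and 5 in 252 ways, or 126 mirror-image pairs. If the lists are drawn independently and balance is scored symmetrically without other ties, the best-balanced pair is selected with probability 1 - (125/126)^20 = 14.7%. If the realized allocation belongs to that pair, the one-sided p-value cannot fall below about 7.4%. The test therefore supports the primary analysis and cannot replace it.
- **Aim 1:** analyse the site mean of the OT-RN pair.
- **Aim 2:** when the between-arm comparison of sessions is written, base it on site-level summaries.

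The cost is SAP wording and a few lines of code, with no new data. The intervals will be wider, as shown above, but that is the precision that ten sites provide without covariate gains.

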### **Study Instruments**

Discuss the particulars of the research instruments, questionnaires and other evaluation instruments in detail. Provide validation documentation and or procedures to be used to validate instruments. For well known and generally accepted test instruments the detail here can be brief. More detail may be required for a novel or new instrument. For ethnographic studies identify any study instruments to be used (i.e. for deception studies) and describe in detail where, when and how the study will be conducted and who or what are the subjects of study. Note: For more information on how to conduct ethical and valid ethnographic research, follow the link For oral histories or interviews provide the general framework for questioning and means of data collection. If interviews or groups settings are to be audio taped or video taped describe in detail the conditions under which it will take place. Include a copy of any novel or new test instruments with the IRB submission. All enrolled Trinity PACE trainees will complete baseline pre and post training surveys to assess changes in knowledge and assess satisfaction with the training including the NOMAD framework measure which has been adapted with COPE-specific language.

Demographics (age, gender, race, ethnicity, education and years employed by Trinity) will be collected at baseline for all trainees as well. At baseline, one representative from each site will complete a baseline questionnaire about their site's staff-participant ratio and location characteristics (urban rural, suburban). At baseline, study team members will collect demographics (age, gender, race, ethnicity, education, address, age, living arrangement, employment status, neighborhood characteristics, relationship status and duration of care) of caregivers and persons with dementia and self-reported data on incomes and feelings of financial strain. The following study instruments will be administered to all caregivers at baseline and four months. The Caregiver Relationship Scale will assess the relationship of person with dementia and their caregiver. The LSNS-R: Caregiver Social Support measure will gather self-reported data about the quality of support received from family and friends. The health-related quality of life and functional ability of the person with dementia will be collected using the Short-Form 36 (SF-36). Caregivers will report the dependence level and functional ability of the person with dementia via the CAFU. Caregivers will report on the presence of a set of behaviors exhibited by the person with dementia, the severity and frequency of those behaviors and level of distress felt by the caregiver via an adapted version of the NPI-Q (Neuropsychiatric Inventory). Caregivers will self-report the sense of capability and confidence in providing support to person with dementia via the Short Sense of Competence Questionnaire (SSCQ): 7 items. Caregivers will self-report feelings of depression via the PHQ-9. Caregivers will self-report their perceptions of caregiving skills via the Caregiver Mastery. Caregivers will self-report their perception of change in wellbeing via Perceived Change for Better Index (13 items). Caregivers will report the quality of life of the person with dementia via QOL-AD CG. Caregivers will self-report their confidence level taking care of PLWD via the CG Confidence in Using Activities and Caregiver Confidence in Medical Sign/Symptom Management. Caregivers will self-report perceived burden as a caregiver of person with dementia via Caregiver Burden. Caregivers intervention progress will be tracked and collected via an intervention instrument called the summary of problem areas and caregiver progress.
